5.1.2 Exclusion Criteria

- 1. Clinically significant blood glucose abnormalities that preclude a satisfactory FDG PET/CT scan.
- 2. Previous history of external radiotherapy where prior radiotherapy fields are anticipated to overlap with the radiotherapy fields required for the present study.
- 3. Diffuse metastatic process (leptomeningeal disease, peritoneal carcinomatosis, diffuse bone marrow involvement, etc.)
- 4. PET-avid structures not intended for radiation are within 2cm from target on third-party diagnostic PET/CT as assessed by investigator
- 5. Known allergy to FDG
- 6. Known psychiatric or substance abuse disorder that would interfere with conduct of the study
- 7. Pregnant, breast-feeding or expecting to conceive during the study
- 8. Patient weight exceeding the weight limit outlined per IFU

- 9. For Cohort II only: Patients with pacemakers and other implantable devices who are deemed to be at high risk by the treating physician for complications secondary to radiotherapy
- 10. For Cohort II only: Patients with bone lesions who are determined to be high risk by the treating physician for pathologic fracture prior to beginning radiotherapy
- 11. For Cohort II only: Active inflammatory bowel disease, scleroderma, or other disorder deemed to be a risk factor for excess toxicity in the area of treatment by the treating physician.

5.2 Withdrawal and Replacement of Subjects

While study withdrawal is discouraged, subjects may withdraw their consent at any time, with or without reason and without prejudice to further treatment. Subject's withdrawal of consent must be documented. Withdrawn subjects will not undergo any additional follow-up, nor will they be replaced.

Subjects whose imaging sessions do not adhere to the sequence and timing defined in the protocol (see section 6. Study Procedures) may be replaced at the discretion of the investigator in consultation with the SMC. The reasons for not adhering could be due to patient choice or due to scheduling issues or device operation delays with the RefleXion or third party PET/CT equipment. All subjects will be accounted for in the study tables and all subject data will be reviewed by the SMC.

5.3 Enrollment Controls

Enrollment will be monitored to ensure that no more than the maximum planned number of subjects is enrolled. An electronic data capture system will be used, and the system will be set to automatically notify the Project Manager and/or CRA of all subject enrollments being entered within the system. Study sites will be notified as enrollment nears maximum allowed.

6. STUDY PROCEDURES

6.1 Written Informed Consent

Written Informed Consent must be obtained for all subjects who are screened and meet the general inclusion/exclusion criteria prior to enrollment.

The subject or the subject's Legally Authorized Representative (LAR) will be asked to sign the Informed Consent form before any study-specific tests or procedures are performed. The Informed Consent Form (ICF) must be approved by the study Institutional Review Board (IRB). Electronic informed consent procedures may be utilized if approved by the IRB and consistent with FDA guidance on use of electronic informed consent in clinical investigations. Study personnel should explain that even if a subject agrees to participate in the study and signs an Informed Consent Form, imaging or other tests may demonstrate that the subject is not a suitable candidate for study participation/treatment. All subjects that have signed

the ICF, met all study eligibility criteria (and none of the exclusion criteria), and present for the RefleXion Imaging-only session will be considered enrolled at the time of FDG administration.

A Screening and Enrollment Log will be maintained by the site to document basic information such as date screened and reason for screen failures for subjects who fail to meet the study eligibility criteria. Screenfailed subjects and their reason(s) for screen failure will be documented and may be entered into the electronic database, but they will not be followed beyond the screening visit, and no further data will be collected/recorded.

Investigator and/or study personnel at the site will review the study requirements with the subject to maximize compliance with the follow-up schedule. Study personnel will instruct subjects to return for study assessments per Study Event Schedule for the applicable cohort the patient is enrolled in.

6.2 Cohort I: RRFD Cohort

6.2.1 Baseline Visit

The following baseline data should be collected within two weeks prior to the Imaging-only PET session for all subjects enrolled in Cohort I and documented in the case report form (CRF):

- Confirmation that all inclusion criteria and none of the exclusion criteria are met.
- Demographics, medical history and physical exam
- Complete Blood Count (CBC)
- Comprehensive Metabolic Panel (CMP)
- ECOG performance status
- Blood glucose
- Urinalysis
- Pregnancy test (required for women of child-bearing potential only; within 14 days prior to the initiation of study scans.)

For patients undergoing systemic therapy at the time of enrollment, decisions regarding whether to continue the systemic therapy or undergo a wash-out will be made by the treating physician in accordance with standard of care for combining radiation and drug therapy.

Additionally, a Sim CT should be obtained within two weeks prior to the PET Imaging-only session if not already planned to be obtained as standard of care. Any additional institutional guidelines must be followed regarding negative pregnancy testing in patients about to undergo radiation therapy.

6.2.2 PET Imaging-Only Session, BgRT Treatment Planning, and Quality Assurance

All subjects enrolled in Cohort I will undergo a PET Imaging-only session including a single injection of the applicable FDG dose. Standard-of-care Sim CT images of subjects who are dispositioned to have SBRT will be collected and utilized for the PET Imaging-only session. For subjects who do not have a Sim (4D)CT within two weeks prior to the PET Imaging-only session and are not planned to undergo a Sim-CT for SBRT (e.g. follow-up patients), a Sim (4D)CT obtained as a part of the study protocol within two weeks prior to the PET Imaging-only session the Sim-CT will be used to outline structures necessary for treatment planning including target volumes, organs-at-risk, and the biology-tracking zone.

Once the structures have been delineated and imported into the RefleXion treatment planning system, a BgRT plan is initiated, and the patient can return to the site to undergo passive PET collection on the RMRS system (the PET Imaging-only session). The patient will undergo FDG injection in accordance with standard diagnostic PET/CT protocols. Prior to FDG injection, patients should be fasting for 4-6 hours. A blood glucose measurement will be obtained prior to FDG injection to confirm a level less than or equal to 200 mg/dL. Patients will be rescheduled should the blood glucose value exceed this threshold. After injection the patients should be resting in the uptake area for 60 minutes (±15min).

After the uptake period, patient set-up will include positioning patients on the RefleXion system couch in the treatment position, followed by immobilization (if necessary) and rough alignment using lasers and tattoos. A localization kVCT scan will be performed for refining anatomical alignment in the region of interest and to localize the treatment target area. Sim CT images will be registered with the kVCT to propagate contoured volumes. Specifically, the BTZ will be overlaid digitally on the kVCT images once positioning is completed. A RMRS PET Imaging-only session will then be performed over the 12-20 minutes depending on the size of region of interest. The resulting PET dataset will be transmitted to the RefleXion treatment planning workstation.

Immediately following the RMRS PET imaging session, subjects will be imaged again with a third-party PET/CT in the same treatment position. A second dose of FDG will not be administered for the scan immediately following the RMRS PET Imaging-only session. Sites will make every effort to minimize the time between two scans. To ensure adequate FDG activity, third-party PET scan will be initiated within 180 minutes after the FDG injection. In the unlikely event that third-party PET scan cannot be initiated within 180 minutes, third-party scan can be completed with a separate FDG injection 24 to 96 hours after the initial FDG injection in the same treatment position as per the RMRS PET scan.

Data collected during the RMRS PET Imaging-only and third-party PET/CT scans will be documented on the appropriate CRF and will include the time of FDG injection, start and end times for RMRS PET and third-party diagnostic PET/CT scans. Sites will be provided with instructions for how images should be collected and submitted to RefleXion Medical within five days of the PET Imaging-only session. AEs will be assessed by using Common Terminology Criteria for Adverse Events (CTCAE) v5 at 72±24 hours after the end of PET Imaging-only session.

After the Imaging-only PET dataset is transmitted to the RefleXion treatment planning workstation, BgRT treatment planning can be completed with dose calculation and optimization employing the BgRT

algorithm as described in the BgRT User Manual. Scoring of a successful BgRT plan requires positive localization at the RMRS device during the PET Imaging-only session; reaching the necessary quantitative thresholds (i.e. Activity Concentration and NTS); and meeting coverage goals for target and avoidance goals for OARs. In Cohort I, physician intent, which includes radiotherapy dose and coverage goals, should match institutional practice for ablative radiation for the tumor type and anatomic region being targeted. Dose constraints are recommended to follow NRG Oncology guidelines. As in conventional radiotherapy planning, dose, fractionation, and volume modifications are allowed if such changes are in accordance with institutional practice for the clinical scenario. Similarly, changes to the BTZ volume are allowed at the time of planning. However, the original BTZ must be utilized for the primary endpoint and secondary imaging endpoints described in section 6.2.3 and 6.2.4 since those endpoints precede treatment planning. The BgRT plan is considered to be successfully completed when approved by physics and the treating physician.

The BgRT physics quality assurance process verifies that the treatment planning system calculated dose in a phantom is equal to the measured dose in the phantom. Once the BgRT plan is ready (optimization and dose calculation are completed and the plan quality meets desired treatment objectives) a Verification Plan is generated in the treatment planning system as described in the BgRT User Manual. As is common practice, this QA plan is generated by taking the calculated treatment plan fluence and projecting the fluence in a forward dose calculation onto the CT image of an ArcCHECK phantom. The QA plan is then delivered to the ArcCHECK phantom. Upon completion of the dose delivery, the accuracy of the plan delivery can be assessed by comparing the dose in the phantom calculated by the treatment planning system with the actual measured dose in the phantom using gamma analysis software provided with the ArcCHECK phantom.

	Screening	PET Imaging-Only	Follow-Up
	&Baseline ¹	Session	(72±24 hours after the
			PET Imaging-only
			session)
Informed Consent ²	x		
Demographics,	x		
Medical History &			
Physical Exam			
CBC	x		
СМР	х		
Blood glucose	x	x	
Urinalysis	x		
ECOG performance	х		
status			
Pregnancy test ³	x		
Sim CT ⁴	x		
(if not done as			
standard of care)			
FDG injection ⁵		x	
(15mCi or 20mCi)			
RMRS PET w/ kVCT		x	
localization ^{4,5}			
Third-party		x	
diagnostic PET/CT ^{4,5}			
AE Assessment ⁶		x	x

Table 1: Cohort I- Study Event Schedule

¹ Baseline Assessments should be completed within 14 days prior to the PET Imaging-only session

² Informed consent is not considered a baseline assessment and has no requirement to be completed within a specific time window from study visits

³Women of child-bearing potential only; within 14 days prior to the initiation of the study scans.

⁴Images should be de-identified before submitting to RefleXion Medical.

⁵ In the event that third-party PET scan cannot be initiated within 180 minutes of original FDG injection, then the third-party scan can be completed with a separate FDG injection 24 to 96 hours after the initial FDG injection. ⁶AEs to be assessed using Common Terminology Criteria for Adverse Events (CTCAE) v5

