1.3.2 Simulation and Treatment Planning

If BgRT candidacy is considered, the patient must then undergo a simulation process for radiotherapy treatment planning that collects necessary PET emission data on the RefleXion system. In the workflow, this requires that the patient first undergo a traditional CT simulation which is then followed by a new PET imaging step on the RefleXion system, labeled the PET Imaging-Only Session. In this step, RMRS PET emission data is collected in the same treatment position as was established during the anatomic CT simulation.

The sequencing of CT simulation prior to RMRS PET Imaging-Only Session is necessary because the PET Imaging-Only Session requires an overlay of (4D)CT-defined contours, which act to narrow down the anatomic location for PET emission collection. Specifically, a Biology-tracking zone (BTZ) defined as the motion envelope of the tumor on the (4D)CT image set plus a margin must be delineated ahead of the

PET Imaging-Only Session in order to localize where in the body the target tumor is located. In addition to the BTZ, other CT-defined tumor targets (GTV, CTV, PTV) and nearby organs-at-risk (OARs) are also contoured based upon the CT simulation images.

At the PET Imaging-Only Session itself, the patient is injected with FDG and, after an approximate 1-hour uptake period, is setup in the RefleXion system in the same treatment position as was used during CT simulation. The same immobilization devices used during the CT simulation are likewise deployed. Next, the patient's alignment is fine-tuned with CT-guidance using RefleXion's on-board fanbeam kVCT, and the patient is moved on the treatment couch such that the PET detector arcs on the RefleXion system are aligned with the region of interest containing the target tumor.

Next, the PET detector arcs capture PET emission data and generate a PET image. Of note, the time window for imaging relative to the injection must be controlled so that the activity is not too high, which could saturate the detectors, or too low secondary to FDG decay, which would result in inadequate PET activity for BgRT. After the PET emission data is collected, several steps occur to formally assess for BgRT candidacy and, if appropriate, to generate a high quality BgRT treatment plan.

At the RMRS Device:

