1. The patient's (4D)CT-defined BTZ is overlaid on the RMRS PET image. This overlay is enabled by the prior CT alignment step, which indexes the CT anatomy obtained in the treatment position on the day of the PET Imaging-Only Session to the CT anatomy obtained previously at CT simulation. Once the PET image is formed, the radiation oncologist confirms that the tumor in the PET image can, in fact, be visualized and localized to within the BTZ as expected.

Notably, the BTZ overlay is a volume based upon (4D)CT images generated on a commercial, thirdparty Sim CT device. Therefore, in addition to capturing PET information for the BgRT algorithm, this step also acts to verify the location accuracy of the RMRS PET image as compared to an external reference standard.

The patient may leave the department once the RMRS PET image is acquired and validated by the radiation oncologist. Provided that localization/visualization of the tumor PET image within the BTZ is confirmed by the radiation oncologist, the PET data is then transmitted to the treatment planning system (TPS) for the next steps.

At the Treatment Planning System Console:

2. Specific quantitative parameters of the tumor PET image are calculated by the treatment planning software to determine whether BgRT is a viable option for BgRT planning and treatment delivery.

These quantitative criteria for BgRT candidacy include:

a. Activity Concentration: Greater than 5 kBq/ml

b. Tumor signal-to-background ratio as measured by the Normalized Target Signal (NTS): Greater than 2.7

Notably, these values are indexed to RefleXion's software and hardware architecture as well as the patient's radiotherapy treatment position. Therefore, they cannot be extrapolated from a third-party PET/CT.

- 3. The physician also qualitatively assesses the following:
 - a. FDG-avid OARs are outside the BTZ
 - b. No FDG-avid structures aside from the tumor are in the BTZ.

If all of the qualitative and quantitative criteria are met, the PET emission data from within the BTZ can be incorporated into the treatment planning software for the BgRT algorithm's dose calculations. As described in detail in the Investigator Brochure (IB) and summarized in section 1.2, the algorithm acts to optimize a firing matrix that converts PET projections to a machine-deliverable fluence such that the fluence in turn meets traditional radiotherapy dose objectives, such as coverage goals for the target and avoidance metrics for OARs.

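### Section 5.2 lets a Cohort I subject be replaced for a timing deviation after the Activity Concentration is known, and section 6.2.2 sets no latest RMRS scan start, so the RRFD count is open to outcome-aware replacement.

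*Combined protocol and SAP*

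**What the plan says.** Section 1.3.2 states that "the time window for imaging relative to the injection must be controlled so that the activity is not too high", and adds that activity must not be too low through decay either. It gives no number.

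Section 6.2.2 bounds two intervals in Cohort I:

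- **Rest after injection:** "After injection the patients should be resting in the uptake area for 60 minutes (±15min", that is 45 to 75 min. Couch set-up, alignment and a kVCT follow, then an RMRS scan of 12 to 20 min. No latest RMRS start is given.
- **Comparator scan:** "third-party PET scan will be initiated within 180 minutes after the FDG injection". If that is missed, the "third-party scan can be completed with a separate FDG injection 24 to 96 hours after the initial FDG injection".

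Section 5.2 is the only text that links timing to who is counted. "Subjects whose imaging sessions do not adhere to the sequence and timing defined in the protocol" "may be replaced at the discretion of the investigator in consultation with the SMC". The reasons it lists include "device operation delays with the RefleXion or third party PET/CT equipment". It also says that all subjects appear in the study tables and that the SMC reviews all subject data.

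Sections 4.2 and 13.1.1 set the dose rule. Two of the first three readings below 5 kBq/ml stop 15 mCi, and at least five of six at or above it make 15 mCi the RRFD. Neither section states an evaluability condition for Cohort I. Cohort II does have one, in sections 4.3 and 13.1.2.

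**The concern.** The study is open-label. Section 1.3.2 says "Specific quantitative parameters of the tumor PET image are calculated by the treatment planning software", so the reading can be available soon after the session. The SMC, which adjudicates after every three patients or fewer, includes site and sponsor staff. Under section 5.2 as written, these parties may replace a subject for a timing deviation when they already know whether the reading was above or below 5 kBq/ml.

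A deviation in the third-party scan is enough to open that option, although the RMRS reading precedes that scan and is unaffected by it. A delay in the RMRS scan itself has no stated limit to be judged against, so whether a session counts as late is also a matter of judgement.

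The count decides the Cohort I primary endpoint and the FDG dose for every Cohort II subject. If low readings are replaced more readily than high ones, 15 mCi is accepted more often than the table in section 13.1.1 implies. If low readings from late scans are kept, the error runs towards 20 mCi, against the ALARA aim in section 4.2.

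**Working it through.** **1. The plan's own figures.** With true below-threshold rate p, 15 mCi is accepted if at most one of six readings is low:

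A(p) = (1 − p)^6 + 6p(1 − p)^5

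This gives 0.886, 0.655, 0.420 and 0.233 at p = 10%, 20%, 30% and 40%, matching section 13.1.1. Stopping at two low readings in the first three does not change these values, because such a path already has two failures.

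**2. What the timing text implies for the RMRS start.** The third-party scan follows the RMRS scan and must start by 180 min. The latest RMRS start is therefore 180 − 20 = 160 min to 180 − 12 = 168 min, ignoring transfer time. The re-injection fallback removes even this limit and leaves the late RMRS reading in place.

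**3. Outcome-aware replacement.** Two assumptions, neither from the documents: a share d of sessions has a qualifying deviation, unrelated to the reading, and every low reading among them is replaced by a new draw, again if necessary. High readings are never replaced. The low rate among counted subjects is then

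q = p(1 − d) / (1 − pd)

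and acceptance is A(q).

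| True rate p | A(p), no replacement | d = 10%: q, A(q) | d = 20%: q, A(q) |
|---|---|---|---|
| 10% | 0.886 | 0.0909, 0.903 | 0.0816, 0.920 |
| 20% | 0.655 | 0.1837, 0.695 | 0.1667, 0.737 |
| 30% | 0.420 | 0.2784, 0.468 | 0.2553, 0.521 |
| 40% | 0.233 | 0.3750, 0.274 | 0.3478, 0.323 |

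Example at p = 30%, d = 10%: q = 0.27/0.97 = 0.2784. For given d this is an upper bound, since it supposes that every opportunity is used.

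**4. How often one subject could decide the dose.** Exactly two of six are low with probability 0.098, 0.246 and 0.324 at p = 10%, 20% and 30%. For replacement to matter, at least one of those two must also have a deviation, which has probability 1 − (1 − d)². At d = 10% this is 0.19, and the products are 0.019, 0.047 and 0.062.

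**5. Replacement decided on time alone.** If lateness is unrelated to tumour activity and the decision ignores the reading, then q = p and the section 13.1.1 values hold.

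**The case against.** Several points on the other side have weight.

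- **A late RMRS reading need not be counted.** A reader might infer that a scan delayed by set-up or a device fault breaches no limit and so automatically enters the count. The documents do not say so: section 5.2 names RefleXion device delays among the reasons for replacement. What remains is that no threshold says when such a delay qualifies.
- **One subject does not decide the dose as often as it may seem.** A reader might take the 0.098 to 0.324 in step 4 as that chance. It is not, because a low subject must also have a deviation.
- **Replacement has an ordinary meaning.** Section 5.2 contrasts withdrawn subjects, who are not replaced, with off-timing subjects, who may be. The natural reading is that the new subject takes the slot in the count. This is fair, and it is also why the timing of the decision matters.
- **A rule may exist elsewhere.** The SMC charter, Figure 5 and the site imaging instructions are not available here, and section 13.3 leaves the SAP to be finalised later. A rule there cannot be excluded, but section 5.2 itself grants the discretion without referring to one.
- **The count is not a strict test.** Section 4.2 bases the RRFD primarily on it and lets the SMC move to 20 mCi on secondary grounds. That wider discretion would remain. It would correct a wrongly accepted 15 mCi only if the secondary results were also poor.
- **The consequences are bounded.** No BgRT beam is directed at patients, activity is checked again at each PreScan, and Cohort II endpoint 5a reports the share of imaging sessions reaching 5 kBq/ml. A poor choice of 15 mCi would tend to show there, but only after Cohort II subjects had been injected at that dose.

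Recorded times, full tabulation and SMC review make a replacement visible afterwards. They do not fix beforehand which readings count.

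**Conclusion.** The concern holds, and the plan should be changed. Section 5.2 permits replacement with knowledge of the result, including for delays that have no bearing on the reading, and section 6.2.2 leaves the relevant interval without a limit.

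The effect is modest where 15 mCi performs well (at most 0.017 to 0.034 added to acceptance at a 10% true rate). It is larger where the dose is doubtful (0.048 to 0.101 at 30%). These sizes rest on the assumed 10% to 20% of deviating sessions and on every low one being replaced. The documents give no deviation frequency, and nothing in them suggests that replacement would in fact be used selectively. The probability table in section 13.1.1 is correct; the issue is whether the count will be formed in the way the table supposes.

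**What to change.** 1. **Section 6.2.2:** state one maximum time from FDG injection to RMRS scan start, set by the sponsor from device requirements, and use that interval alone as the timing criterion for the count. As an example only, the 75 min upper rest limit plus 30 min for set-up and kVCT gives 105 min. A 20 min scan then ends by 125 min, leaving 55 min before the third-party limit. The 30 min has no basis in the documents. Rest time should not be a second exclusion criterion, since that would discard scans started within the limit.
2. **Sections 4.2 and 5.2:** a session beyond the limit is replaced and does not count among the first three or the six. Someone who has not seen the Activity Concentration decides this from the CRF times, with the same rule for high and low readings.
3. **Section 5.2:** a third-party scan deviation alone never removes an RMRS reading from the count.
4. **SMC report:** show the count with all scanned subjects as a sensitivity check.

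The cost is protocol wording and an occasional replaced session, which section 5.2 already permits. The injection and scan times are already on the CRF. Keep the planned maximum of 12. If both dose levels need six subjects there is no spare place, as is already true of replacements now, and the SMC should then be told that the count is short. Raising enrolment to 15 is not a cheap remedy: the chance of 12 evaluable subjects would be 0.94 if 10% of sessions were out of window, but only 0.65 if 20% were.
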